8.2.3 Electrocardiograms

- Single 12-lead ECG will be obtained as outlined in the SoA (see [Section 1.3](#)) using an ECG machine that automatically calculates the heart rate and measures PR, QRS, QT, and QTcF intervals. Refer to [Section 7](#) for QTcF withdrawal criteria and any additional QTcF readings that may be necessary. The ECG should be recorded after 10 minutes of rest in the supine position.

8.2.4 Clinical safety laboratory assessments

- See Appendix 2 ([Section 10.2](#)) for the list of clinical laboratory tests to be performed and to the SoA (see [Section 1.3](#)) for the timing and frequency.

- The Investigator must review the laboratory report, document this review, and record any clinically relevant changes occurring during the study in the AE section of the CRF. The laboratory reports must be filed with the source documents. Clinically significant abnormal laboratory findings are those which are not associated with the underlying disease, unless judged by the Investigator to be more severe than expected for the participant's condition.
- All laboratory tests with values considered clinically significantly abnormal during participation in the study or within 12 weeks after the last dose of study intervention should be repeated until the values return to normal or baseline or are no longer considered clinically significant by the Investigator or medical monitor.
 - If such values do not return to normal/baseline within a period of time judged reasonable by the Investigator, the etiology should be identified and the Sponsor notified,
 - All protocol-required laboratory assessments, as defined in Appendix 2 ([Section 10.2](#)), must be conducted in accordance with the laboratory manual and the SoA (see [Section 1.3](#)),
 - If laboratory values from non-protocol specified laboratory assessments performed at the institution's local laboratory require a change in participant management or are considered clinically significant by the Investigator (eg, SAE or AE or dose modification), then the results must be recorded in the CRF.

8.3 ADVERSE EVENTS AND SERIOUS ADVERSE EVENTS

Adverse event of special interest

An AESI is an AE (serious or nonserious) of scientific and medical concern specific to the Sponsor's product or program, for which ongoing monitoring and immediate notification by the Investigator to the Sponsor is required. Such events may require further investigation in order to characterize and understand them. Adverse events of special interest may be added, modified or removed during a study by protocol amendment.

For these AESIs, the Sponsor will be informed immediately (ie, within 24 hours), per SAE notification described in [Section 10.3](#), even if not fulfilling a seriousness criterion, using the corresponding pages in the CRF (to be sent) or screens in the eCRF. If an SAE or any AESI of anaphylactic reactions or systemic allergic reactions that are related to IMP and require treatment, or severe injection site reactions lasting longer than 24 hours, occurs in a participant, blood samples should be collected for determination of functional dupilumab concentration, and ADA assessment at or near the onset and completion of the occurrence of the event, if possible.

- Anaphylactic reactions.
- Systemic hypersensitivity reactions.
- Helminthic infections.
- Any severe type of conjunctivitis or blepharitis.
- Keratitis.

- Clinically symptomatic eosinophilia (or eosinophilia associated with clinical symptoms).
- Pregnancy of a female subject entered in a study as well as pregnancy occurring in a female partner of a male subject entered in a study with IMP/NIMP;
 - Pregnancy occurring in a female participant entered in the clinical trial or in a female partner of a male participant entered in the clinical trial. It will be qualified as an SAE only if it fulfills one of the seriousness criteria,
 - In the event of pregnancy in a female participant, IMP should be discontinued,
 - Follow-up of the pregnancy in a female participant or in a female partner of a male participant is mandatory until the outcome has been determined,
 - Abnormal pregnancy outcomes (eg, spontaneous abortion, fetal death, stillbirth, congenital anomalies, ectopic pregnancy) are considered SAEs.
- Significant ALT elevation
 - ALT >5 x ULN in participants with baseline ALT ≤ 2 x ULN;
OR
 - ALT >8 x ULN if baseline ALT >2 x ULN.
- Symptomatic overdose (serious or nonserious) with IMP/NIMP
 - An overdose (accidental or intentional) with the IMP is an event suspected by the Investigator or spontaneously notified by the participant and defined as at least twice the intended dose during an interval of less than 11 days. The circumstances (ie, accidental or intentional) should be clearly specified in the verbatim and symptoms, if any, entered on separate AE forms.
 - An overdose (accidental or intentional) with any NIMP is an event suspected by the Investigator or spontaneously notified by the participant and defined as at least twice the maximum prescribed daily dose, within the intended therapeutic interval. The circumstances (ie, accidental or intentional) should be clearly specified in the overdose form.

The definitions of an AE or SAE can be found in Appendix 3 ([Section 10.3](#)).

Adverse events will be reported by the participant (or, when appropriate, by a caregiver, surrogate, or the participant's legally authorized representative).

The Investigator and any qualified designees are responsible for detecting, documenting, and recording events that meet the definition of an AE or SAE and remain responsible for following up AEs that are serious, considered related to the study intervention or study procedures, or that caused the participant to discontinue the study intervention (see [Section 7](#)).

8.3.1 Time period and frequency for collecting AE and SAE information

All AEs, serious or nonserious, will be collected from the signing of the ICF until the EOS visit at the time points specified in the SoA ([Section 1.3](#)).

All SAEs and AESI will be recorded and reported to the Sponsor or designee immediately and under no circumstance should this exceed 24 hours, as indicated in Appendix 3 ([Section 10.3](#)). The Investigator will submit any updated SAE data to the Sponsor within 24 hours of it being available.

Investigators are not obligated to actively seek AE or SAE after conclusion of the study participation. However, if the Investigator learns of any SAE, including a death, at any time after a participant has been discharged from the study, and he/she considers the event to be reasonably related to the study intervention or study participation, the Investigator must promptly notify the Sponsor.

8.3.2 Method of detecting AEs and SAEs

The method of recording, evaluating, and assessing causality of AE and SAE and the procedures for completing and transmitting SAE reports are provided in Appendix 3 ([Section 10.3](#)).

Care will be taken not to introduce bias when detecting AEs and/or SAEs. Open-ended and non-leading verbal questioning of the participant is the preferred method to inquire about AE occurrences.

8.3.3 Follow-up of AEs and SAEs

After the initial AE/AESI/SAE report, the Investigator is required to proactively follow each participant at subsequent visits/contacts. At the pre-specified study end-date, all SAEs and nonserious AESI (as defined in [Section 8.3](#)) will be followed until resolution, stabilization, the event is otherwise explained, or the participant is lost to follow-up (as defined in [Section 7.3](#)). Further information on follow-up procedures is given in Appendix 3 ([Section 10.3](#)).

8.3.4 Regulatory reporting requirements for SAEs

- Prompt notification by the Investigator to the Sponsor of a SAE is essential so that legal obligations and ethical responsibilities towards the safety of participants and the safety of a study intervention under clinical investigation are met.
- The Sponsor has a legal responsibility to notify both the local regulatory authority and other regulatory agencies about the safety of a study intervention under clinical investigation. The Sponsor will comply with country-specific regulatory requirements relating to safety reporting to the regulatory authority, Institutional Review Boards (IRB)/Independent Ethics Committees (IEC), and Investigators.
- Investigator safety reports must be prepared for suspected unexpected serious adverse reactions (SUSAR) according to local regulatory requirements and Sponsor policy and forwarded to Investigators as necessary.
- Adverse events that are considered expected will be specified in the reference safety information.
- An Investigator who receives an Investigator safety report describing a SAE or other specific safety information (eg, summary or listing of SAEs) from the Sponsor will review and then file it along with the IB and will notify the IRB/IEC, if appropriate according to local requirements.

8.3.5 Pregnancy

- Details of all pregnancies in female participants and female partners of male participants will be collected after the start of study intervention and until the outcome has been determined.
- If a pregnancy is reported, the Investigator should inform the Sponsor within 24 hours of learning of the pregnancy and should follow the procedures outlined in Appendix 4 ([Section 10.4](#)).
- Abnormal pregnancy outcomes (eg, spontaneous abortion, fetal death, stillbirth, congenital anomalies, ectopic pregnancy) are considered SAEs.

8.3.6 Guidelines for reporting product complaints

Any defect in the IMP/NIMP/device must be reported as soon as possible by the Investigator to the monitoring team that will complete a product complaint form within required timelines.

Appropriate information (eg, samples, labels or documents like pictures or photocopies) related to product identification and to the potential deficiencies may need to be gathered. The Investigator will assess whether or not the quality issue has to be reported together with an AE or SAE.

8.4 TREATMENT OF OVERDOSE

Overdose is an AESI (defined in [Section 8.3](#)). No antidote is available for dupilumab. Sponsor does not recommend specific treatment for an overdose.

In the event of an overdose, the Investigator/treating physician should:

1. Provide symptomatic care.
2. Contact the Medical Monitor immediately.
3. Closely monitor the participant for any AE/SAE and laboratory abnormalities until dupilumab can no longer be detected systemically.
4. Obtain a plasma sample for PK analysis as soon as possible if requested by the Medical Monitor (determined on a case-by-case basis).
5. Document appropriately in the CRF.

Decisions regarding dose interruptions will be made by the Investigator in consultation with the Medical Monitor based on the clinical evaluation of the participant.

8.5 PHARMACOKINETICS

8.5.1 Systemic drug concentration and antidrug antibodies

8.5.1.1 Sampling time

Blood samples will be collected for determination of functional dupilumab and anti-dupilumab antibodies in serum as specified in the SoA (Section 1.3). Special procedures for collection, storage, and shipping of serum are described in separate operational manuals. The date of collection should be recorded in the eCRF.

8.5.1.2 Handling procedures

Special procedures for collection, storage, and shipping of serum are described in separate operational manuals. An overview of handling procedure for samples used in the determination of systemic drug concentration and ADA is provided in [Table 3](#).

Table 3 - Summary of handling procedures

Sample type	Functional dupilumab	Anti-dupilumab antibody
Matrix	Serum	Serum
Blood sample volume	5 mL	5 mL
Anticoagulant	None	None
Blood handling procedures	See Operational Manual	See Operational Manual
Serum aliquot split	2 aliquots	2 aliquots
Storage conditions	<6 months: below -20°C <24 months: below -80°C (preferred)	<6 months: below -20°C <24 months: below -80°C (preferred)
Serum shipment condition	In dry ice	In dry ice

8.5.1.3 Bioanalytic method

Serum PK and ADA samples will be assayed using validated methods as described in [Table 4](#).

Table 4 - Summary of bioanalytical methods for functional dupilumab and anti-dupilumab antibodies

Note: In the event of any SAE, any AE of severe injection site reaction lasting longer than 24 hours, or any AESI of anaphylactic reaction or systemic allergic reaction that is related to IMP and require treatment, PK and ADA samples will be collected at or near the onset of the event for

any additional analysis if required or for archival purposes. The exact date and time of sample collection must be recorded and entered into the database by the central laboratory. An unscheduled systemic drug concentration page in the eCRF must be completed as well. If necessary for safety monitoring, additional PK and ADA samples may be collected after the EOS Visit until resolution of AE.

Specifically for PK, any changes in the timing or addition of time points for any planned study assessments must be documented and approved by the relevant study team member and then archived in the Sponsor and site study files, but will not constitute a protocol amendment. The IRB/IEC will be informed of any safety issues that require alteration of the safety monitoring scheme or amendment of the ICF.

8.6 PHARMACODYNAMICS

See [Section 8.8](#) for IgE measurement. No other PD parameters will be evaluated in this study.

8.7 GENETICS

For those participants who consent to the optional pharmacogenetic/pharmacogenomic sample collection section of the ICF, blood samples for exploratory genetic analysis of DNA or RNA will be collected and stored for possible future use (see [Section 10.5](#)). Participation is optional. Participants who do not wish to participate in the genetic research may still participate in the study.

In the event of DNA extraction failure, a replacement genetic blood sample may be requested from the participant.

Details on processes for collection and shipment and destruction of these samples can be found in the laboratory manual.

8.8 BIOMARKERS

- Venous blood samples will be collected for measurement of total serum IgE. Total IgE will be measured using validated quantitative methods.
- Optional samples for biomarker research that should be collected from participants in the study with their consent are the following:
 - Serum and plasma: samples will be collected and stored for possible future analysis of potential biomarkers of drug response, disease activity, safety, and type 2 inflammation,
 - Skin biopsy (sub-study): samples will be taken from lesion and non-lesion skin using punch biopsy; gene expression and immunohistological analyses may be used to investigate drug response, disease activity, and type 2 inflammation.

Plasma, serum and skin biopsy samples may be stored for a maximum of 5 years, and DNA or RNA samples for 15 years (or according to local regulations) following the last participant's last visit for the study at a facility selected by the Sponsor.

8.9 MEDICAL RESOURCE UTILIZATION AND HEALTH ECONOMICS

Number of missed school/work days collection is described in [Section 8.1.9](#).

9 STATISTICAL CONSIDERATIONS

9.1 STATISTICAL HYPOTHESES

The statistical hypotheses for comparing dupilumab to placebo on the primary endpoint of the proportion of participants with WI-NRS reduction of ≥ 4 (minimally important difference) at Week 24 are as follows:

- Null hypothesis H0: No treatment difference between dupilumab and placebo.
- Alternative hypothesis H1: There is a treatment difference between dupilumab and placebo.

The statistical hypotheses to be tested on secondary endpoints can be specified similarly to those on the primary endpoint.

9.2 SAMPLE SIZE DETERMINATION

The primary endpoint is the proportion of participants with WI-NRS reduction of ≥ 4 from baseline to Week 24. By assuming the response rate is [REDACTED] and [REDACTED] in placebo and dupilumab respectively, 56 participants/arm will provide 90% power to detect the difference of [REDACTED] between dupilumab and placebo with Fisher exact test at 2-sided level of 0.05. Assuming 15% drop out during treatment, the target is to randomize 75 participants/arm with a cap of up to 10% of participants in the atopic population having mild active AD.

Approximately 150 participants will be randomized 1:1. This corresponds to approximately 75 participants that will be randomly assigned to each intervention arm.

The sample size calculation was performed using SAS 9.4 power procedure. The assumptions were based on the effect of dupilumab versus placebo in WI-NRS reduction ≥ 4 at Week 16 observed in patients with moderate to severe AD as seen in studies of R668-AD-1334 (Solo1) and R668-AD-1416 (Solo2).

Participants will be randomized to dupilumab or placebo in 1:1 ratio with stratification factors of documented history of atopy (atopic or non-atopic, see definition in [Section 6.3](#)), stable use of TCS/TCI (yes or no), and country/territory code. Both the atopic and the non-atopic PN population will be capped at 60% of the total enrolled population.

9.3 POPULATIONS FOR ANALYSES

For purposes of analysis, the following populations are defined ([Table 5](#)):

Table 5 - Populations for analyses

Population	Description
Screened	All participants who sign the ICF.
Randomized	The randomized population includes all participants with a treatment kit number allocated and recorded in the IRT database, and regardless of whether the treatment kit was used or not. Participants treated without being randomized will not be considered randomized and will not be included in any efficacy population.
Intent-to-treat (ITT)	All randomized participants analyzed according to the treatment group allocated by randomization regardless if treatment kit is used or not
Efficacy	The analysis population for the efficacy endpoints will be the ITT population.
Safety	All participants randomly assigned to study intervention and who take at least 1 dose of study intervention. Participants will be analyzed according to the intervention they actually received. Randomized participants for whom it is unclear whether they took the study medication will be included in the safety population as randomized. For participants who accidentally receive different treatment from the planned, the actual intervention allocation for as-treated analysis will be the dupilumab group. The PD analyses will be performed on the safety population.
Pharmacokinetic (PK)	The PK population includes all participants in the safety population with at least one non-missing result for functional dupilumab concentration in serum after first dose of the study treatment. Participants will be analyzed according to the intervention actually received.
Antidrug antibody (ADA)	ADA population includes all participants in the safety population who have at least one non-missing ADA result after first dose of the study treatment. Participants will be analyzed according to the intervention actually received.

ADA: antidrug antibody; ICF: informed consent form; IRT: interactive response technology; ITT: intent to treat; PD: pharmacodynamics; PK: pharmacokinetic.

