1 INTRODUCTION

1.1 STUDY DESIGN

This study is a multi-center, 24-week treatment, parallel group, double-blind, randomized, placebo-controlled study to evaluate the use of dupilumab in participants with prurigo nodularis (PN) inadequately controlled on topical prescription therapies or when those therapies are not advisable. The study will assess the effect of dupilumab on itch improvement as well as its effect on PN lesions, on participants' health-related quality of life (HRQoL), anxiety and depression, sleep quality, skin pain, and overall health status.

After 2-4 weeks of screening, participants will be centrally randomized using a permuted block randomization schedule via Interactive Voice Response System/Interactive Web Response System (IVRS/IWRS) in a 1:1 randomization ratio to dupilumab 300 mg q2w or matching placebo. Randomization will be stratified by documented history of atopy (atopic or non-atopic), stable use of topical corticosteroids (TCS)/topical calcineurin inhibitors (TCI) (yes or no), and country/territory code.

A total of approximately 150 participants will be randomized to two treatment arms (75 participants/arm). The number of participants with active mild AD upon study entry will represent up to 10% of the atopic participants. Both the atopic and the non-atopic PN populations will each be capped at 60% of the total enrolled population.

The study duration consists of the following periods:

- Screening period (2-4 weeks)
- Randomized IMP intervention period (24 weeks)
- Follow-up period (12 weeks).

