3 ANALYSIS POPULATIONS

The following populations for analyses are defined:

Table 4 - Populations for analyses

Population	Description
Screened	All participants who sign the ICF.
Randomized	The randomized population includes all participants with a treatment kit number allocated and recorded in the interactive response technology (IRT) database, and regardless of whether the treatment kit was used or not. Participants treated without being randomized will not be considered randomized and will not be included in any efficacy population.
Intent-to-treat (ITT)	All randomized participants analyzed according to the intervention group allocated by randomization regardless if treatment kit is used or not
Efficacy	The ITT population
Safety	All participants randomly assigned to study intervention and who take at least 1 dose of study intervention. Participants will be analyzed according to the intervention they actually received. Randomized participants for whom it is unclear whether they took the study medication will be included in the safety population as randomized. For participants who accidentally receive different treatment from the planned, the actual intervention allocation for as-treated analysis will be the dupilumab group. The PD analyses will be performed on the safety population.
Pharmacokinetic (PK)	The PK population includes all participants in the safety population with at least one non-missing result for functional dupilumab concentration in serum after first dose of the study treatment. Participants will be analyzed according to the intervention actually received.
Antidrug antibody (ADA)	ADA population includes all participants in the safety population who have at least one non-missing ADA result after first dose of the study treatment. Participants will be analyzed according to the intervention actually received.

ADA: antidrug antibody; ICF: informed consent form; ITT: intent to treat; PD: pharmacodynamics; PK: pharmacokinetic.

Participants exposed to study intervention before or without being randomized will not be considered randomized and will not be included in any analysis population. The safety experience of these participants will be reported separately.

Randomized participants for whom it is unclear whether they took the study intervention will be considered as exposed and will be included in the safety population as randomized.

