For any participant randomized more than once, only the data associated with the first randomization will be used in any analysis population. The safety experience associated with any later randomization will be reported separately.

For participants receiving more than one study intervention (placebo and dupilumab) during the study, the intervention group for as-treated analysis will be the dupilumab group.

Regarding the COVID-19 pandemic, additional summaries by COVID-19 subgroups (ie, impacted by the COVID-19 pandemic and NOT impacted by the COVID-19 pandemic) will be provided to assess the impact of COVID-19 on treatment effect. Participants impacted by the COVID-19 pandemic are defined as randomized participants with any critical or major deviation related to COVID-19 or who permanently discontinued study intervention or study due to COVID-19.

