4.7 SAFETY ANALYSES

All safety analyses will be performed on the safety population as defined in [Section 3](#), unless otherwise specified, using the following common rules:

- The analysis of the safety variables will be descriptive, and no testing is planned.
- Safety data in participants who do not belong to the safety population (eg, exposed but not randomized) will be provided separately.

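### The as-treated rule in the Safety row assigns mis-treated participants to dupilumab without requiring that any dupilumab was received

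*Protocol*

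**What the plan says.** The Safety row of Protocol section 9.3, Table 5, contains two allocation rules that matter here. SAP section 3, Table 4, carries the same two.

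- The general rule: "Participants will be analyzed according to the intervention they actually received".
- The mis-treatment rule, for anyone given something other than planned by accident: "the actual intervention allocation for as-treated analysis will be the dupilumab group".

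A separate sentence in the row keeps participants whose intake is unclear in the group to which they were randomized. The row also directs the PD analyses to the safety population.

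Below Table 4 the SAP adds a rule of narrower scope. It begins "For participants receiving more than one study intervention (placebo and dupilumab) during the study" and places those participants in the dupilumab group. The protocol has no such text.

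The PK and ADA rows each state their own rule, "Participants will be analyzed according to the intervention actually received", with no dupilumab default. SAP section 4.7 says "All safety analyses will be performed on the safety population as defined in" section 3, and that "The analysis of the safety variables will be descriptive, and no testing is planned".

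**The concern.** The mis-treatment rule is triggered by any departure from the planned treatment, in either direction, and always gives the same answer. For a participant randomized to dupilumab who received only placebo, the general rule gives placebo and the mis-treatment rule gives dupilumab. The row thus contradicts itself on a participant who had no exposure to the drug.

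A population definition should give each participant one group before unblinding. Here a programmer who follows the table literally would count an unexposed participant in the dupilumab adverse event, laboratory and total IgE summaries. One who follows the general rule, or the SAP text below the table, would not. In expectation the literal reading mixes placebo experience into the dupilumab column and so blunts any real difference between the groups.

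**Working it through.** The plan states no figure on this point, so there is none to reproduce. The check is a comparison of the rules case by case, followed by an illustration of size.

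**Rules compared**

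| Participant | General rule | Mis-treatment sentence (both tables) | SAP text below Table 4 |
|---|---|---|---|
| (a) Randomized to placebo, received only dupilumab | Dupilumab | Dupilumab | Not addressed |
| (b) Either arm, received both | Not decisive | Dupilumab | Dupilumab |
| (c) Randomized to dupilumab, received only placebo | **Placebo** | **Dupilumab** | Not addressed |

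The conflict is confined to case (c). Within the SAP, the table sentence adds nothing in (a), which the general rule settles, or in (b), which the text below the table settles. The only case in which it changes the result is (c), where the result is wrong. In the protocol the sentence also serves as the only tie-break for (b), so there it should be replaced rather than deleted.

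**Where the label is used**

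- All safety summaries (SAP 4.7).
- Total IgE, which is summarized in the safety population and plotted by intervention group (SAP 4.8.3).
- Not efficacy, which is ITT as randomized.
- Not PK or ADA grouping, which follows those rows' own rule.

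**Size**

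Inputs: 75 per arm (SAP 1.1: "A total of approximately 150 participants will be randomized to two treatment arms (75 participants/arm"). Assumptions not taken from the documents: everyone randomized is exposed, *k* participants fall in case (c), there are no other dosing errors, and the event probabilities are as given below.

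Denominators (dupilumab/placebo): the literal rule gives 75/75, and grouping by treatment received gives (75 − *k*)/(75 + *k*). For *k* = 1 that is 74/76; for *k* = 3, 72/78; for *k* = 5, 70/80.

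Share of the dupilumab group: *k*/75, so 1/75 = 1.3% for one participant.

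Expected dupilumab rate under the literal rule: [(75 − *k*) × p_D + *k* × p_P] / 75. Subtracting p_P gives an expected difference of (p_D − p_P) × (75 − *k*)/75.

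| *k* | Factor | Assumed 20% v 10% (true difference 10.0 points) | Assumed 10% v 5% (true difference 5.0 points) |
|---|---|---|---|
| 1 | 74/75 | 9.87 | 4.93 |
| 3 | 72/75 | 9.60 | 4.80 |
| 5 | 70/75 | 9.33 | 4.67 |

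For example, with *k* = 1: (74 × 0.20 + 1 × 0.10)/75 = 14.9/75 = 19.87%, and 19.87 − 10 = 9.87 points.

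**Direction**

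The same factor applies when the event is more frequent on placebo. With 10% on dupilumab and 20% on placebo, the literal dupilumab rate is (74 × 0.10 + 1 × 0.20)/75 = 10.13%, so the dupilumab rate rises and the difference again shrinks, to 9.87 points. In a single realization it can go either way. If 7 of 74 truly exposed participants have an event (9.5%), adding a placebo-only participant gives 8/75 = 10.7% if that person had the event and 7/75 = 9.3% if not.

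**The case against.** The best reply is that the intent is plain. Protocol section 9.4 leaves the description of the analysis populations to the SAP. The SAP's text below Table 4, taken with the general rule, handles all three cases sensibly, and the table sentence reads naturally as shorthand for the same tie-break. That probably is what was meant. But the SAP's own table carries the broad sentence, nothing says that the later text limits it, and the later text is silent on placebo-only exposure. The protocol has only the broad version.

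The second reply is that case (c) is remote, and this stands. Kits are allocated centrally and hold one syringe each. Two injections on Day 1 and one every two weeks from Week 2 to Week 22 make 2 + 11 = 13 syringes for a completer. A dispensing error would usually produce mixed exposure, where the sentence works. Placebo-only exposure needs every kit used to be wrong, which is realistic mainly after very early discontinuation.

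The third reply, that nothing inferential is touched, also stands: efficacy is analysed as randomized and safety is descriptive.

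Two stronger readings are tempting and should not be adopted:

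- A reader might infer that the participant also enters the dupilumab PK and ADA summaries, with values below quantification set to half the limit (the SAP 4.8.1 rule for drug-treated participants) instead of zero. The documents do not support this. Being drawn from the safety population decides who is included; the PK and ADA rows set the group by treatment received, and a placebo-only participant is not drug-treated.
- A reader might infer that the error always makes dupilumab look safer. It does so in expectation only for events more frequent on dupilumab. For events more frequent on placebo it raises the dupilumab rate, and in a single case it can go either way.

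**Conclusion.** The point holds as a wording defect. As written, the Safety row of both tables misallocates a participant randomized to dupilumab who received only placebo, and it contradicts the general rule in the same row. The SAP's mixed-exposure text softens this but does not remove it.

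The consequence is small and limited to the descriptive safety summaries and the total IgE summaries. One such participant is 1.3% of the planned dupilumab group and shrinks an expected difference by the factor 74/75, for instance from 10.0 to 9.87 points at assumed rates of 20% and 10%. These figures rest on 75 exposed per arm and on illustrative event rates. The documents give no mis-dosing rate, so no expected count can be stated beyond saying that the case should be rare. It is a minor correction, worth making because it is cheap and removes an ambiguity before unblinding.

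**What to change.** In the Safety row of Protocol Table 5 and SAP Table 4, replace the mis-treatment sentence with: *participants who received at least one dose of dupilumab are analysed in the dupilumab group; participants who received only placebo are analysed in the placebo group.*

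This settles cases (a), (b) and (c), agrees with the general rule and is consistent with the SAP text below Table 4, which can stay. Keep the existing rule that participants with unclear intake are analysed as randomized.

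The cost is one sentence in the SAP before database lock and one in the protocol at the next amendment. No analysis, sample size or data collection changes, and there is no evident downside.
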